## 176 **5.2 Masking**

- 5.2.1 All patients, anesthesiologists, other health care team members, and investigators who
- are responsible for data collection and follow-ups will be blinded to group allocation.
- 5.2.2 Investigators who are responsible for postoperative follow-up and outcome assessments
- are not involved in anesthesia and perioperative management and have no knowledge of study
- 181 group assignment.
- 5.2.3 Statistical analysis will be performed by an independent statistician.

## 6. Intervention protocol

## 185 6.1 Anesthesia management

- 186 6.1.1 No premedication will be administered.
- 187 6.1.2 Intraoperative monitoring includes electrocardiogram (ECG) and oxygen saturation
- 188 (SpO2) and non-invasive blood pressure.
- 189 6.1.3 All patients will undergo caesarean section under epidural anesthesia and epidural
- puncture will be performed in the left lateral decubitus position. A 16-G Tuohy needle will be
- used for puncture in the L2-3 lumbar intervertebral space. After confirming the epidural space
- by the loss-of-resistance-to-air method, a catheter will be inserted 3-4 cm in a cephalad
- 193 direction.

184

- 6.1.4 A test dose of 1.5% lidocaine 5 ml will be given. After a 5-minute observation, 0.75%
- ropivacaine 10 ml will be given, followed by an infusion of 0.75% ropivacaine at 3-5 ml/h.
- 196 6.1.5 Oxygen will be provided at 5 L·min via a face mask.
- 197 6.1.6 Study drugs will be administered when the targeted upper sensory block level was
- achieved (about 2 minutes before incision). Specifically, esketamine 0.25 mg·kg will be
- administrated intravenously over 1 min for patients in the esketamine group; the same volume
- of normal saline will be injected for patients in the control group.
- 201 6.1.7 At the end of surgery, a patient-controlled epidural analgesia will be attached for
- 202 postoperative analgesia, which is established with 0.2% ropivacaine and programmed to deliver
- a continuous infusion at 2 ml/h.

# 204 **6.2 Remedial measures**

- 205 6.2.1 If the epidural anesthesia is failed, spinal anesthesia or general anesthesia will be
- 206 performed.
- 207 6.2.2 If the anesthesia level of the block is not sufficient, we will continue to add epidural drugs
- in fractions until the level of the block reaches at least T6.
- 209 6.2.3 The above measures will be recorded.

210

# 211 7. Data collection

- 212 **7.1 Baseline data**
- 213 7.1.1 Demographic parameters, pregestational comorbidity, number of gravidity and
- 214 parturitions, duration of gestation, and ASA classification.
- 215 7.1.2 Pain intensity at rest will be assessed with the numeric rating scale (NRS; an 11-point
- scale where 0=no pain and 10=the worst pain) before anesthesia.
- 7.1.3 Maternal sedation level will be assessed with the Ramsay Sedation Scale (1=restlessness;
- 2=completely awake, quiet and cooperative; 3= drowsiness but responding to verbal commands;

- 4=light asleep but responding to touch or pain; 5= asleep but slowly responding to touch or
- pain; 6=deeply asleep and does not respond) before anesthesia.

# 221 7.2 Intraoperative data

- 7.2.1 Durations of anesthesia and surgery, fluid balance (including fluid infusion, estimated
- blood loss, and urine output), use of vasopressors.
- 7.2.2 Time intervals from study drug administration to neonatal delivery and from uterine
- 225 incision to neonatal delivery.
- 226 7.2.3 Pain intensity at rest will be assessed with the NRS at the following timepoints: after
- 227 anesthesia (before study drug administration), surgical incision (2 min after study drug
- administration), 5 min after study drug administration, immediately after fetal delivery (about
- 229 10 min after esketamine), and end of surgery.
- 7.2.4 Maternal sedation level will be assessed with the Ramsay Sedation Scale at the following
- 231 timepoints: after anesthesia (before study drug administration), surgical incision (2 min after
- 232 study drug administration), 5 min after study drug administration, immediately after fetal
- 233 delivery (about 10 min after esketamine), and end of surgery.
- 7.2.5 Neonatal data including sex, birth weight, and Apgar scores at 1 and 5 minutes after
- 235 delivery.
- 7.2.6 Immediately after childbirth, blood samples will be collected from artery of mothers and
- from umbilical artery and vein of fetuses in the esketamine group (in selected participants) and
- stored in a -20°C refrigerator. Esketamine concentrations were measured with the reverse phase
- 239 high-performance liquid chromatography (RP-HPLC).

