# 251 8.1 Primary outcome

- Our co-primary outcomes include maternal pain intensity and sedation score immediately after
- fetal delivery (about 10 min after esketamine). Pain intensity will be assessed with the NRS.

- 254 Maternal sedation level will be assessed with the Ramsay Sedation Scale.
- 255 **8.2 Secondary outcomes**
- 8.2.1 Maternal pain intensity as assessed with the NRS at the following timepoints: surgical
- 257 incision (2 min after study drug administration), 5 min after study drug administration, end of
- surgery, 6 h after surgery, and 12 h after the surgery.
- 8.2.2 Maternal sedation level as assessed with the Ramsay Sedation Scale at the following
- 260 timepoints: surgical incision (2 min after study drug administration), 5 min after study drug
- administration, end of surgery, 6 h after surgery, and 12 h after the surgery.
- 262 8.2.3 Neonatal Appar score assessed at 1 and 5 minutes after birth.
- 263 8.2.4 Postnatal umbilical vein blood gas pH value.
- 264 8.3 Other outcomes
- 8.3.1 Mean blood pressure (MBP), heart rate (HR), and pulse oxygen saturation (SpO2)
- 266 measured before anesthesia, immediately after anesthesia, surgical incision (2 min after study
- drug administration), 5 min after study drug administration, immediately after fetal delivery
- 268 (10 min after study drug administration), end of surgery, and 1 h after surgery.
- 269 8.3.2 The requirement of neonatal ward admission and length of hospital stay.
- 270 8.3.3 Plasma concentrations of esketamine in maternal blood, neonatal umbilical venous blood
- and umbilical arterial blood after birth.

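### Sampling for esketamine levels is confined to selected esketamine-group women at the moment both co-primary outcomes are scored, so the draw can reveal the arm of each sampled woman

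*Combined protocol and SAP*

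**What the plan says.** Protocol section 7.2.6 begins "Immediately after childbirth, blood samples will be collected from artery of mothers and" continues "from umbilical artery and vein of fetuses in the esketamine group (in selected participants) and" then covers storage and the assay. The purpose is the plasma concentration outcome in 8.3.3 (SAP 3.3.3). How many women are selected, by whom and by what rule is not stated.

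Section 8.1 reads "Our co-primary outcomes include maternal pain intensity and sedation score immediately after" fetal delivery, about 10 minutes after the study drug. Pain is the woman's own NRS rating at rest (7.2.3). Sedation is an observer's Ramsay rating (7.2.4).

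On blinding, 5.2.1 covers "All patients, anesthesiologists, other health care team members, and investigators who" adds that they "are responsible for data collection and follow-ups will be blinded to group allocation". Section 5.2.2 says that those doing postoperative follow-up and outcome assessment "are not involved in anesthesia and perioperative management and have no knowledge of study" group. Section 11.2 places unmasking after database lock.

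Three further provisions bear on the point. In 5.1.2 a coordinator at each center passes on the randomization result. In 5.1.4 those who give the study drug do not assess outcomes. In 5.1.3 an anesthesiologist is assigned to both anesthesia and data collection.

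**The concern.** A procedure done in one arm only, in the operating room, at the primary time point, cannot be squared with the blinding that 5.2.1 promises. Someone must know the allocation during surgery in order to choose women from the esketamine group. Anyone present who knows the protocol and sees the draw then learns the arm of that woman. Both co-primary outcomes are subjective, so expectation can move them.

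There is a second, more conditional route. If the maternal draw comes before scoring and needs a new arterial puncture, it could raise the pain score or rouse a sedated woman, in the esketamine arm only.

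The two routes can act in opposite directions, and the trial data could not separate them afterwards. The planned pain difference is only 0.3 NRS points, so a small artefact can be a sizeable fraction of it.

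**Working it through.** **Which draws reveal the arm**

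| Draw | Arms, as far as stated | Reveals the arm? |
|---|---|---|
| Maternal artery (7.2.6) | Esketamine, selected women | Yes |
| Umbilical artery (7.2.6) | Esketamine, selected women | Yes, as far as stated |
| Umbilical vein | Both: vein pH is a secondary outcome (8.2.4) compared between groups (13.5.2.1) | No |
| No sample taken | Controls and unselected esketamine women | No |

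**Is the time point the same?** Sections 7.2.6 and 8.1 both place the event immediately after delivery. Neither says which comes first.

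**Is a new puncture needed?** Section 6.1.2 lists ECG, oxygen saturation and non-invasive blood pressure, so no arterial line is planned. A new puncture is therefore likely, but it is not stated.

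**The plan's own figure**
- Inputs (protocol 3.2, SAP 2): difference 0.3, SDs 0.85 and 1.23, alpha 5%, power 90%.
- Sum of variances: 0.85² + 1.23² = 0.7225 + 1.5129 = 2.2354.
- Normal approximation, two-sided 5%: n = (1.960 + 1.2816)² × 2.2354 / 0.3² = 261 per group. An unequal-variance t test gives 263, the stated figure.

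**Sensitivity of the pain comparison**
- Evaluable per group: 300 × 0.9 = 270.
- Standard error: √(2.2354 / 270) = 0.0910.
- Two-sided 0.025 for each co-primary (protocol 13.1.4) gives z = 2.2414.
- With no bias: 0.3 / 0.0910 − 2.2414 = 1.06, so power is 85%.
- If a fraction f of the esketamine arm is sampled and each sampled score shifts by s points, the mean difference moves by f × s. Both f and s are assumptions; the documents give neither.

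| f | s | Shift f × s | Share of 0.3 | Power if the shift opposes the effect | Type I error if there is no true effect |
|---|---|---|---|---|---|
| 0 | – | 0 | 0% | 85% | 0.025 |
| 5% | 0.5 | 0.025 | 8% | 78% | 0.031 |
| 10% | 0.5 | 0.05 | 17% | 69% | 0.048 |
| 10% | 1 | 0.10 | 33% | 48% | 0.127 |

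Example, last row: (0.30 − 0.10) / 0.0910 − 2.2414 = −0.04, which is 48% power. With no true effect and a shift of 0.10, 0.10 / 0.0910 − 2.2414 = −1.14, which gives about 0.127.

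These figures use a normal approximation for means, whereas the planned test is Mann-Whitney. They cover the NRS only; the documents give no planning values for Ramsay. The starting power of 85% rather than 90% arises because the sample size was computed at 0.05 while each test uses 0.025. That is a separate matter.

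**The case against.** The plan has safeguards. Those who give the drug do not assess outcomes (5.1.4), and assessors stand apart from anesthesia and perioperative care (5.2.2). The coordinator already handles the allocation (5.1.2), so choosing whom to sample need not unblind anyone new. Scoring may well come before sampling. The subset may be small, in which case the effect on the primary comparison is minor, as the 5% row shows.

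Much of this stands, and it limits the size of the concern. It does not remove it. The delivery scores have to be taken in the operating room, where the blood is drawn, and nothing puts the assessor out of sight. Section 5.1.3 leaves it unclear who collects the intraoperative data.

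A reader might infer more than the documents support:
- **That the whole esketamine arm is unblinded.** Only selected women are sampled, and the absence of a sample does not identify a control.
- **That any cord sampling gives the arm away.** Vein blood is needed in both arms for the pH outcome. Cord sampling is also no stimulus to the mother.
- **That a painful needle stick coincides with the pain score.** Neither the method of access nor the order is stated.
- **That a large loss of power is established.** The larger losses depend entirely on an assumed fraction and an assumed shift.

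**Conclusion.** The conflict is real. As written, 7.2.6 lets anyone who sees the maternal arterial draw, or as far as stated the umbilical arterial draw, infer esketamine for that woman, contrary to 5.2.1 and 11.2. It does so at the time point of both co-primary outcomes. This is more than a missing detail, because no way of following 7.2.6 as it stands keeps the people at the draw blind.

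Its size cannot be fixed from the documents. Over the range shown it runs from minor (85% to 78% power) to serious (48% power, or type I error of about 0.13). The direction is also unknown: knowledge of the arm could favour esketamine, while a puncture before scoring would tend to raise pain and reduce sedation in that arm.

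This should be fixed, with medium confidence.

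**What to change.** Amend 7.2.6 as follows:

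1. Record the delivery NRS and Ramsay scores on the case report form before any blood is drawn.
2. State the number to be sampled and pre-mark the subset by sequence number in both arms, so that entry into the subset does not depend on the arm.
3. Draw the same cord samples, artery and vein, in the marked subset of both arms. Assay only the esketamine samples.
4. Take the maternal sample after the primary scores, out of view of those who score outcomes. Use staff who already hold the allocation and do not assess outcomes (5.1.2, 5.1.4). Keep the record of it from assessors of later pain, sedation and adverse events until unmasking.

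Item 4 is needed because the maternal draw stays confined to the esketamine arm. Without concealment it could still unblind the scores at end of surgery, 6 h and 12 h, and the adverse-event assessments.

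The cost is a short amendment, with no change to the sample size, no extra assays and no puncture of control mothers. Some control cord samples are discarded, and the maternal sample is taken slightly later. One weakness remains: the sampled mother may still infer her own arm, which affects her later scores but not the delivery scores.

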## 240 7.3 Postoperative data

- 7.3.1 Routine anesthetic follow-up after caesarean section.
- 7.3.2 Maternal psychiatric symptoms that may be caused by experimental drugs.
- 7.3.3 Pain intensity at rest will be assessed with the NRS at the following timepoints: 6 h after
- surgery, and 12 h after the surgery.
- 7.3.4 Maternal sedation level will be assessed with the Ramsay Sedation Scale at the following
- 246 timepoints: 6 h after surgery, and 12 h after the surgery.
- 7.3.5 Admission to neonatal ward or neonatal intensive care unit.
- 248 7.3.6 Length of hospital stay after surgery.

#### **8. Outcomes**

249

# 251 8.1 Primary outcome

- Our co-primary outcomes include maternal pain intensity and sedation score immediately after
- fetal delivery (about 10 min after esketamine). Pain intensity will be assessed with the NRS.

- 254 Maternal sedation level will be assessed with the Ramsay Sedation Scale.
- 255 **8.2 Secondary outcomes**
- 8.2.1 Maternal pain intensity as assessed with the NRS at the following timepoints: surgical
- 257 incision (2 min after study drug administration), 5 min after study drug administration, end of
- surgery, 6 h after surgery, and 12 h after the surgery.
- 8.2.2 Maternal sedation level as assessed with the Ramsay Sedation Scale at the following
- 260 timepoints: surgical incision (2 min after study drug administration), 5 min after study drug
- administration, end of surgery, 6 h after surgery, and 12 h after the surgery.
- 262 8.2.3 Neonatal Appar score assessed at 1 and 5 minutes after birth.
- 263 8.2.4 Postnatal umbilical vein blood gas pH value.
- 264 8.3 Other outcomes
- 8.3.1 Mean blood pressure (MBP), heart rate (HR), and pulse oxygen saturation (SpO2)
- 266 measured before anesthesia, immediately after anesthesia, surgical incision (2 min after study
- drug administration), 5 min after study drug administration, immediately after fetal delivery
- 268 (10 min after study drug administration), end of surgery, and 1 h after surgery.
- 269 8.3.2 The requirement of neonatal ward admission and length of hospital stay.
- 270 8.3.3 Plasma concentrations of esketamine in maternal blood, neonatal umbilical venous blood
- and umbilical arterial blood after birth.

# 273 **9. Adverse events**

**9.1 Definition** 

- 275 An adverse event indicates any unpredictable, unfavorable medical event that is associated with
- any medical intervention and occurs during the study period. It can be related to the study
- 277 intervention or otherwise. It can manifest as any uncomfortable signs (including abnormal
- 278 laboratory findings), symptoms, or transient morbidity.
- 279 9.2 Predicted adverse events in this study
- 9.2.1 Hypotension was defined as systolic pressure decrease <20% of baseline.
- 9.2.2 Hypertension was defined as systolic pressure increase >20% of baseline.
- 9.2.3 Bradycardia was defined as heart rate <60 bpm.
- 283 9.2.4 Tachycardia was defined as heart rate >100 bpm.
- 9.2.5 Desaturation was defined as oxygen saturation <90%.
- 285 9.2.6 Nausea and vomiting.
- 286 9.2.7 Neurological and mental signs and symptoms (such as lethargy, diplopia, dizziness,
- 287 headache, nightmare, hallucination, anxiety, and irritability) and nystagmus.

288 9.2.8 Adverse events will be managed according to routine practice.

289

290

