#### 355 13.5 Efficacy analysis

356 13.5.1 Evaluation of primary endpoints

- For the primary outcomes (maternal pain intensity and sedation score immediately after fetal
- delivery), the differences between group will be analyzed using Mann-Whitney U test. Median
- differences and 95% CIs will be calculated with the Hodges-Lehmann estimators.
- 360 13.5.2 Evaluation of secondary and other endpoints
- 361 13.5.2.1 Discrete variables (maternal pain intensity and sedation score during the perinatal
- period, neonatal Apgar scores, and umbilical vein pH) will be analyzed with the Mann-Whitney
- 363 U tests. Median differences and 95% CIs will be calculated with the Hodges-Lehmann
- 364 estimators. Missing data will not be replaced.
- 13.5.2.2 Categorical variables (neonatal ward admission proportion) will be analyzed using the
- chi-square tests, continuity correction chi-square tests or Fisher exact tests. The rate differences
- and 95% CIs will be provided. Missing data will not be replaced.
- 368 13.5.2.3 Time-to-event variables (length of hospital stay after surgery) will be analyzed with
- the Kaplan-Meier estimators with differences between groups assessed by the log-rank test;
- Cox proportional hazards models will be used to calculate HRs and 95% CIs.
- 371 13.6 Safety analysis
- 372 13.5.1 Describe the occurrence of adverse events in each group.
- 13.5.2 Describe the management of adverse events when appropriate.
- 374 13.5.3 Describe the occurrence of severe adverse events.
- 375 13.5.4 The rates of adverse events and/or managements between the two groups will be
- compared with Chi-Square test, continuity correction Chi-Square test or Fisher exact test.
- 377 13.5.5 Missing data will not be replaced.

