# 4.4 Intra- and postoperative variables

- Numeric variables will be analyzed using the independent-samples t tests or Mann-Whitney U
- tests; categorical variables will be analyzed using the chi-square tests, continuity correction

- 554 chi-square tests or Fisher exact tests. Missing data will not be replaced.
- 555 **4.5 Efficacy analysis**
- 556 4.5.1 Evaluation of primary endpoints
- For the primary outcomes (maternal pain intensity and sedation score immediately after fetal
- delivery), the differences between group will be analyzed using Mann-Whitney U test. Median
- differences and 95% CIs will be calculated with the Hodges-Lehmann estimators.
- 560 4.5.2 Evaluation of secondary and other endpoints
- 4.5.1 Discrete variables (maternal pain intensity and sedation score during the perinatal period,
- neonatal Apgar scores, and umbilical vein pH) will be analyzed with the Mann-Whitney U tests.
- Median differences and 95% CIs will be calculated with the Hodges-Lehmann estimators.
- Missing data will not be replaced.
- 4.5.2 Categorical variables (neonatal ward admission proportion) will be analyzed using the
- chi-square tests, continuity correction chi-square tests or Fisher exact tests. The rate differences
- and 95% CIs will be provided. Missing data will not be replaced.
- 4.5.3 Time-to-event variables (length of hospital stay after surgery) will be analyzed with the
- Kaplan-Meier estimators with differences between groups assessed by the log-rank test; Cox
- proportional hazards models will be used to calculate HRs and 95% CIs.
- 571 4.6 Safety analysis

- 4.6.1 Describe the occurrence of adverse events in each group.
- 573 4.6.2 Describe the management of adverse events when appropriate.
- 4.6.3 Describe the occurrence of severe adverse events.
- 575 4.6.4 The rates of adverse events and/or managements between the two groups will be
- 576 compared with Chi-Square test, continuity correction Chi-Square test or Fisher exact test.
- 577 4.6.5 Missing data will not be replaced.

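### The hypotension definition in protocol 9.2.1 has its inequality facing the opposite way to the paired hypertension item, so read literally small falls count as events and falls above 20% do not

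*Combined protocol and SAP*

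**What the plan says.** Protocol 9.2 lists the predicted adverse events. Item 9.2.1 reads: "Hypotension was defined as systolic pressure decrease <20% of baseline". Item 9.2.2, directly below it, reads: "Hypertension was defined as systolic pressure increase >20% of baseline". The other numeric items are bradycardia (heart rate below 60 bpm), tachycardia (above 100 bpm) and desaturation (below 90%).

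The general definition in 9.1 begins: "An adverse event indicates any unpredictable, unfavorable medical event that is associated with".

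Hypotension is defined nowhere else. The SAP describes itself as a copy from the protocol and does not restate the adverse event definitions.

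The definition is used in the safety analysis. SAP 4.6.1 asks to "Describe the occurrence of adverse events in each group". Under protocol 13.6 (the item numbered 13.5.4) and SAP 4.6.4, "The rates of adverse events and/or managements between the two groups will be" compared by a chi-square test, with or without continuity correction, or by Fisher's exact test.

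**The concern.** The sign in 9.2.1 points to the normal side of the threshold. The other four numeric items in the list all point to the abnormal side. A rule that counts small falls and leaves out large ones also conflicts with the idea in 9.1 that an adverse event is unfavourable.

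This is the only definition of hypotension that a data manager or analyst can find, and the event rate it produces belongs to a planned between-arm comparison. The Background calls the efficacy and safety of intravenous esketamine before childbirth still unclear, so the safety tables matter to the reader. If the sentence were followed literally, the hypotension row would count the wrong women, and the comparison could show no difference, or the opposite one, when larger falls do differ between arms.

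**Working it through.** No sample size, power or alpha figure enters this point, so there is no plan figure to reproduce. The check has two parts.

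**1. Classification under each rule**

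Let f = (baseline systolic − observed systolic) / baseline systolic.

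- As written (9.2.1): event if 0 < f < 0.20.
- Same direction as 9.2.2: event if f > 0.20.

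The documents give no baseline systolic pressure, so 120 mmHg is assumed. Observed pressure is 120 × (1 − f).

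| Fall | Pressure (mmHg) | Event as written | Event in the direction of 9.2.2 |
|---|---|---|---|
| 5% | 114 | yes | no |
| 10% | 108 | yes | no |
| 19% | 97.2 | yes | no |
| 20% | 96 | no | no |
| 25% | 90 | no | yes |
| 30% | 84 | no | yes |
| 40% | 72 | no | yes |

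The rule is proportional, so the classification is the same at assumed baselines of 110 and 130 mmHg. Every case flips except exactly 20%, which neither strict inequality covers.

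One other literal reading is a fall to below 20% of baseline. At 120 mmHg that means below 0.20 × 120 = 24 mmHg. It is unworkable and would still miss large falls.

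**2. What this could do to the arm comparison**

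Assume the percentage fall is normal with mean m and SD 10 points in each arm. Means and SD are assumptions; the arms are labelled A and B because the documents do not say which would fall further. Φ is the standard normal distribution function.

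- As written: P(0 < fall < 20) = Φ((20 − m)/10) − Φ((0 − m)/10).
- Direction of 9.2.2: P(fall > 20) = 1 − Φ((20 − m)/10).

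Worked for m = 8 and m = 12:

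- As written, m = 8: Φ(1.2) − Φ(−0.8) = 0.673. m = 12: Φ(0.8) − Φ(−1.2) = 0.673.
- Direction of 9.2.2, m = 8: 1 − Φ(1.2) = 0.115. m = 12: 1 − Φ(0.8) = 0.212.

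Worked for m = 5 and m = 10:

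- As written, m = 5: Φ(1.5) − Φ(−0.5) = 0.933 − 0.309 = 0.625 (unrounded 0.6247). m = 10: Φ(1) − Φ(−1) = 0.683.
- Direction of 9.2.2, m = 5: 1 − Φ(1.5) = 0.067. m = 10: 1 − Φ(1) = 0.159.

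| Mean fall, A vs B | Rate as written, A vs B | Rate of falls above 20%, A vs B | Effect on the difference |
|---|---|---|---|
| 5% vs 10% | 62.5% vs 68.3% | 6.7% vs 15.9% | shrinks (5.8 against 9.2 points) |
| 8% vs 12% | 67.3% vs 67.3% | 11.5% vs 21.2% | vanishes |
| 15% vs 10% | 62.5% vs 68.3% | 30.9% vs 15.9% | reverses |
| 20% vs 15% | 47.7% vs 62.5% | 50.0% vs 30.9% | reverses |
| 25% vs 18% | 30.2% vs 54.3% | 69.1% vs 42.1% | reverses |

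The pattern has a simple cause. With equal SDs, the rate as written depends only on how far the mean lies from 10, the middle of the 0 to 20 window, and is highest at 10. The rate of falls above 20% rises steadily with the mean. Means placed evenly around 10 therefore tie, and once both means are at or above 10 the arms swap order.

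**The case against.** The strongest reply is that this is an evident slip of the sign. The next line shows the direction, and trained staff are unlikely to record a 1% fall as hypotension and ignore a 40% fall. That is plausible, and it means the effect on collected data is unknown. It does not make the sentence usable as a pre-specified definition, because it relies on every centre and the analyst departing from the text in the same unstated way. A misread character in the PDF cannot be fully excluded, but the sign on the next line was read normally.

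The reach is also narrow, and this stands:

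- Hypotension is not among the primary, secondary or other outcomes in section 8.
- Mean blood pressure is scheduled at seven timepoints (8.3.1) and vasopressor use is recorded (7.2.1). Neither depends on 9.2.1, so haemodynamic information remains.
- Adverse events are managed by routine practice (9.2.8), so the definition is not a stated treatment trigger.

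A reader might infer that the trial's hypotension counts are wrong. The documents do not support this: they show no case report form field and no derivation code, and staff may record the event directly.

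A reader might also infer from the 67.3% tie that a real difference would necessarily disappear, or that events would be overcounted by a fixed multiple. Neither follows. The tie arises because 8 and 12 lie evenly around 10, and the other assumed means give a smaller or a reversed difference. None of these rates is an estimate for this trial.

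**Conclusion.** The concern holds, with limited reach. The definition in 9.2.1 is wrong as written: it contradicts 9.2.2 and sits badly with 9.1, and nothing in the protocol or SAP corrects it. This part needs no assumption beyond reading the inequality.

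The consequence is conditional. If the rule is applied literally, the hypotension rate in the adverse event comparison is wrong, and the arm difference can shrink, vanish or reverse. The size depends on blood pressure distributions that the documents do not give; the figures above rest on assumed normal falls with an equal SD of 10 points and are illustrations only.

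The co-primary pain and sedation outcomes, the sample size, mean blood pressure and vasopressor data do not depend on it. It is an inconsistency between two definitions, confined to one row of the safety comparison, and it does not put the trial's main conclusions in doubt.

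**What to change.** Reconcile 9.2.1 with 9.2.2 so that the inequality runs in the same direction as the document's own paired definition. State how a change of exactly 20% is classed, since at present neither item covers it. The clinical threshold itself is for the sponsor to confirm.

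Then confirm that the case report form, the site instructions and any derivation code use that direction. Check as well whether systolic values are kept in the database: 8.3.1 schedules mean pressure only, so if hypotension is recorded only as yes or no, it may not be possible to re-derive it. Repeating the reconciled definition in SAP 4.6 would give the analyst one place to look.

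The cost is a correction of about one character, a sentence on the boundary, and a check of the form and the code. No change to the sample size, the visits or the primary analysis is needed.

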## 351 13.4 Intra- and postoperative variables

- Numeric variables will be analyzed using the independent-samples t tests or Mann-Whitney U
- 353 tests; categorical variables will be analyzed using the chi-square tests, continuity correction
- 354 chi-square tests or Fisher exact tests. Missing data will not be replaced.

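### The post-epidural, pre-drug hemodynamic reading is collected but not used as a covariate or reference, which costs precision for MBP and HR, and the baseline for the systolic events is not specified

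*Combined protocol and SAP*

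**What the plan says.** **Readings.** Protocol 8.3.1 (SAP 3.3.1) lists "Mean blood pressure (MBP), heart rate (HR), and pulse oxygen saturation (SpO2") as other outcomes, "measured before anesthesia, immediately after anesthesia, surgical incision (2 min after study" drug), and at four later times. The second of these times comes before the study drug: 7.2.3 describes the matching pain assessment as after "anesthesia (before study drug administration), surgical incision (2 min after study drug" administration), and 6.1.6 gives the drug only once the block has reached its target level, about 2 minutes before incision.

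**Analysis.** Protocol 13.5.2 (SAP 4.5.2) covers secondary and other endpoints but names no method for these three variables. That leaves the general rule in 13.4 (SAP 4.4): "Numeric variables will be analyzed using the independent-samples t tests or Mann-Whitney U" tests. No covariate, change score, repeated-measures model, estimated difference or confidence interval is specified for them.

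**Events.** Protocol 9.2.1 reads "Hypotension was defined as systolic pressure decrease <20% of baseline", and 9.2.2 reads "Hypertension was defined as systolic pressure increase >20% of baseline". Neither identifies the baseline reading. Section 7.1 (Baseline data) takes pain on a "scale where 0=no pain and 10=the worst pain) before anesthesia", and sedation at the same time, but does not list blood pressure. The heart-rate events use absolute limits, for example "Tachycardia was defined as heart rate >100 bpm", so the baseline question does not affect them. Event rates are compared between arms by chi-square or Fisher tests (13.6; SAP 4.6.4).

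**The concern.** The drug is given after the block, so the reading that best isolates its hemodynamic effect is the last one before injection. The plan collects it and then leaves it out of the estimation.

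Two things are at stake. For MBP and HR, each post-drug comparison carries between-woman variation that the pre-drug reading could remove. For the systolic events, the reference changes what is counted. A pre-anesthesia reference measures departure from usual pressure, with the epidural's effect included. A pre-drug reference measures change since the injection. With the reference unstated, sites may choose differently, and the hypertension count may respond weakly to a pressor effect.

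**Working it through.** **Inputs.** The documents give no blood-pressure mean, SD, correlation, epidural fall or pressor effect, so every hemodynamic input below is an assumption. The group sizes are the plan's: 263 needed and 300 enrolled per arm (3.2). The 263 reproduces (difference 0.3, SDs 0.85 and 1.23, two-sided 5%, 90% power, unequal-variance t), but it concerns pain and serves here only as a group size.

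**1. Precision for MBP and HR.** With correlation r between the pre-drug and a later reading, adjustment multiplies the CI width by √(1−r²). The equivalent gain in patients is 1/(1−r²) − 1.
- r = 0.5: √0.75 = 0.866, so 13% narrower; 1/0.75 − 1 = 33% more patients.
- r = 0.7: √0.51 = 0.714, so 29% narrower; 1/0.51 − 1 = 96% more patients.

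The difference detectable with 90% power at 263 per arm is (1.96 + 1.28) × SD × √(2/263). For an SD of 8 to 15 mmHg it is 2.3 to 4.2 mmHg unadjusted, 2.0 to 3.7 at r = 0.5, and 1.6 to 3.0 at r = 0.7.

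**2. Bias for MBP and HR.** The epidural's fall comes before the drug in both randomized arms and cancels in expectation. A simulation (2,000 trials, 263 per arm, true effect 5 mmHg, mean epidural fall 12 mmHg) returned 4.96 unadjusted (SE 0.97) and 4.97 adjusted (SE 0.69). Only the standard error changes.

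**3. Systolic events if baseline is pre-anesthesia.** After a fractional fall f, hypertension needs a rise above the pre-drug reading of more than 1.20/(1−f) − 1. For example, 1.20/0.90 − 1 = 33%. Reading 9.2.1 as a fall of more than 20% (an assumption, since its wording is unclear), hypotension needs a post-drug change below 0.80/(1−f) − 1. The rates below assume a drug effect of +10%, SD 10%, and the same f for every woman. Power is the normal approximation at 300 per arm, two-sided 0.05, and is rough where events are very rare.

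| Fall f | Rise needed | Hypertension, control vs esketamine | Power | Hypotension, control vs esketamine | Power |
|---|---|---|---|---|---|
| 5% | 26% | 0.4% vs 5.1% | 94% | 5.7% vs 0.5% | 96% |
| 10% | 33% | 0.04% vs 1.0% | 36% | 13.3% vs 1.7% | >99% |
| 20% | 50% | about 0% vs 0.003% | 3% | 50% vs 16% | >99% |

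With the pre-drug reading as reference, hypertension is 2.3% vs 15.9% (power above 99%).

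**4. Sensitivity to a common fall.** If f varies between women (normal, SD 10 points), hypertension power for mean falls of 5%, 10% and 20% becomes about 99%, 92% and 35%. The loss is in the same direction but much smaller at a 10% fall.

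**5. What a pre-drug reference would count.** A 20% rise from the pre-drug reading puts a woman at (1−f) × 1.20 of her pre-anesthesia pressure: 0.85 × 1.20 = 102% after a 15% fall, and 0.80 × 1.20 = 96% after a 20% fall.

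**The case against.** The strongest reply is that nothing here biases a result and that hemodynamics are only other outcomes. This stands: the case for adjustment is efficiency, and a 5 mmHg difference already has about 97% power or more at 263 per arm for an SD up to 15 mmHg.

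It is also fair that a pre-drug reference has its own fault. Step 5 shows that after a fall of 15-20% it would label a return to about usual pressure as hypertension. It therefore belongs beside the pre-anesthesia version and should not replace it.

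A reader might infer four stronger points, which the documents do not support:
- *That events are measured from a pre-epidural baseline.* Section 7.1 makes this a natural guess, but blood pressure is not listed there. What can be shown is that the reference is unspecified.
- *That the epidural's fall hides a pressor effect in MBP or HR.* It is common to both arms and cancels (step 2).
- *That the drug could look hemodynamically neutral.* In the same model the shift that removes hypertension events sharpens the hypotension comparison (step 3), and vasopressor use is recorded (7.2.1) and compared under 13.4.
- *That the systolic events cannot be derived because 8.3.1 lists mean pressure.* Non-invasive pressure is monitored throughout surgery (6.1.2), and nothing confines event detection to the 8.3.1 readings.

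The post-epidural reading is also not ignored: 13.4 would compare it between arms at its own time. It is unused only as a covariate or reference.

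**Conclusion.** The point holds in two limited parts.

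First, the post-drug MBP and HR comparisons are unbiased but less precise than the collected data allow. Adjustment would narrow the CI by about 13-29%, on an assumed correlation of 0.5-0.7; a weaker correlation would gain less.

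Second, the reference for the systolic events is not defined. If it is the pre-anesthesia reading, the hypertension count becomes less sensitive to a pressor effect. The rise needed follows by arithmetic from the assumed fall (33% for a 10% fall). The loss of power does not have a firm size: at a mean 10% fall it is 36% or about 92%, depending only on whether the fall is identical or varies between women. Other planned comparisons could still show the effect, so this is a gap in one safety count and does not undermine the hemodynamic assessment as a whole.

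**What to change.** 1. In protocol 13.5.2 and SAP 4.5.2, state that at the post-drug times MBP and HR (and SpO2 where its distribution allows) are reported as mean differences with 95% CIs. Estimate them by ANCOVA or a repeated-measures model with the reading listed straight after anesthesia in 8.3.1 as covariate.
2. Drop the between-arm tests at the two pre-drug times. Any difference there in a randomized trial is due to chance.
3. In 9.2.1 and 9.2.2, state which reading is baseline.
4. For the between-arm safety comparison, tabulate post-drug systolic changes from the last pre-drug reading beside the pre-anesthesia version. Label them as change from pre-drug, because after a large fall they may only reflect a return to usual pressure.
5. Keep the systolic value from the same cuff readings that supply the mean.

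The cost is SAP wording and one more number per reading, with no new assessment. The downside is two versions of the pressure events in one table.
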